	Proportion of patients with ≥ 4 -point reduction from baseline after lebrikizumab retreatment among those patients with Pruritus NRS of ≥ 4 -point at baseline	NA	Descriptive statistics	Maintenance W24-48 Escape Population with Baseline Pruritus NRS score at least 4	No comparisons. Every 4 weeks after escape and re-treated by lebrikizumab 250mg Q2W	Secondary analysis

Measure	Variable	Estimand (Section 6.2)	Analysis Method (Section 6.1)	Population (Section 6.1.1)	Comparison/Time Point	Analysis Type
Sleep-loss Score	Percent Change from baseline in Sleep-loss Change from baseline in Sleep-loss	Primary Estimand (Hybrid)	ANCOVA with MCMC-MI	ITT	Leb 250 mg Q2W vs PBO; Week 16 and all scheduled visits in Induction Period	Key secondary analysis: percent change and change, W16; Secondary analysis: other timepoints
		Supportive Estimand (Hypothetical)	MMRM with observed data	ITT	Leb 250 mg Q2W vs PBO; Week 16 and all scheduled visits in Induction Period	Key secondary analysis: percent change and change, W16; Secondary analysis: other timepoints
		Maintenance Supportive Estimand (Hypothetical)	ANCOVA with LOCF	Maintenance Primary Population	Leb 250 mg Q2W vs PBO; Leb 250 mg Q4W vs PBO; all scheduled visits in Maintenance Period	Secondary analysis
	Proportion of patients achieving at least 2-point improvement in Sleep-loss in patients who had baseline Sleep-loss ≥ 2	Primary Estimand (Hybrid)	CMH analysis with MCMC-MI	ITT with Baseline Sleep-loss score at least 2	Leb 250 mg Q2W vs PBO; Week 16 and all scheduled visits in Induction Period	Key secondary analysis: Weeks 16; Secondary analysis: other timepoints
		Supportive Estimand (Composite)	CMH analysis with NRI	ITT with Baseline Sleep-loss score at least 2	Leb 250 mg Q2W vs PBO; Week 16 and all scheduled visits in Induction Period	Supplementary analysis

Measure	Variable	Estimand (Section 6.2)	Analysis Method (Section 6.1)	Population (Section 6.1.1)	Comparison/Time Point	Analysis Type
	Proportion of patients achieving at least 2-point improvement in Sleep-loss in patients who had baseline Sleep-loss ≥ 2	Maintenance Supportive Estimand (Composite)	CMH with NRI	Maintenance Primary Population with Baseline Sleep-loss score at least 2	Leb 250 mg Q2W vs PBO; Leb 250 mg Q4W vs PBO; all scheduled visits in Maintenance Period	Secondary analysis
	Proportion of patients achieving at least 2-point improvement in Sleep-loss in patients who had baseline Sleep-loss ≥ 2	NA	Descriptive statistics	Maintenance W16 Escape Population with Baseline Sleep-loss score at least 2	No comparisons. all scheduled visits in Maintenance Period	Secondary analysis
(Children) Dermatology Life Quality Index (DLQI/ CDLQI)	Change from baseline in DLQI total score	Primary Estimand (Hybrid)	ANCOVA with MCMC-MI	ITT	Leb 250 mg Q2W vs PBO; Week 16 and all scheduled visits in Induction Period	Key secondary analysis: W16 for DLQI chg; Secondary analysis: other timepoints
	Change from baseline in DLQI total score	Supportive Estimand (Hypothetical)	MMRM with observed data	ITT	Leb 250 mg Q2W vs PBO; Week 16 and all scheduled visits in Induction Period	Supplementary analysis for DLQI; Secondary analysis for CDLQI
	Change from baseline in CDLQI total score					
	Change from baseline in DLQI total score	Maintenance Supportive Estimand (Hypothetical)	ANCOVA with LOCF	Maintenance Primary Population	Leb 250 mg Q2W vs PBO; Leb 250 mg Q4W vs PBO; all scheduled visits in Maintenance Period	Secondary analysis
	Change from baseline in CDLQI total score					

Measure	Variable	Estimand (Section 6.2)	Analysis Method (Section 6.1)	Population (Section 6.1.1)	Comparison/Time Point	Analysis Type
	Change from baseline in DLQI total score	NA	Descriptive stats	Maintenance W16 Escape Population	No comparisons. all scheduled visits in Maintenance Period	Secondary analysis
	Change from baseline in CDLQI total score					
	Proportion of patients achieving at least 4-point improvement in DLQI	Primary Estimand (Hybrid)	CMH analysis with MCMC-MI	ITT, ITT with Baseline DLQI score at least 4	Leb 250 mg Q2W vs PBO; Week 16 and all scheduled visits in Induction Period	Key secondary analysis: W16 for ITT with Baseline DLQI score at least 4, Secondary analysis: other timepoints and population
		Supportive Estimand (Composite)	CMH analysis with NRI	ITT with Baseline DLQI score at least 4	Leb 250 mg Q2W vs PBO; Week 16 and all scheduled visits in Induction Period	Supplementary analysis
	Proportion of patients achieving ≥ 4 point improvement in DLQI in patients who had baseline DLQI score ≥ 4	Maintenance Supportive Estimand (Composite)	CMH with NRI	Maintenance Primary Population with baseline DLQI score at least 4	Leb 250 mg Q2W vs PBO; Leb 250 mg Q4W vs PBO; all scheduled visits in Maintenance Period	Secondary analysis
	Proportion of patients achieving ≥ 4 point improvement in DLQI in patients who had baseline DLQI score ≥ 4	NA	Descriptive statistics	Maintenance W16 Escape Population with Baseline DLQI score at least 4	No comparisons. all scheduled visits in Maintenance Period	Secondary analysis

Measure	Variable	Estimand (Section 6.2)	Analysis Method (Section 6.1)	Population (Section 6.1.1)	Comparison/Time Point	Analysis Type
SCORing Atopic Dermatitis (SCORAD)	Change from baseline in SCORAD score Percent change from baseline in SCORAD score	Supportive Estimand (Hypothetical)	ANCOVA with LOCF	ITT	Leb 250 mg Q2W vs PBO; Week 16 and all scheduled visits in Induction Period	Secondary analysis
		Maintenance Supportive Estimand (Hypothetical)	ANCOVA with LOCF	Maintenance Primary Population	Leb 250 mg Q2W vs PBO; Leb 250 mg Q4W vs PBO; all scheduled visits in Maintenance Period	Secondary analysis
		NA	Descriptive stats	Maintenance W16 Escape Population	No comparisons. all scheduled visits in Maintenance Period	Secondary analysis
	Proportion of patients achieving SCORAD75 Proportion of patients achieving SCORAD90	Supportive Estimand (Composite)	CMH analysis with NRI	ITT	Leb 250 mg Q2W vs PBO; Week 16 and all scheduled visits in Induction Period	Secondary analysis
		Maintenance Supportive Estimand (Composite)	CMH with NRI	Maintenance Primary Population	Leb 250 mg Q2W vs PBO; Leb 250 mg Q4W vs PBO; all scheduled visits in Maintenance Period	Secondary analysis
		NA	Descriptive stats	Maintenance W16 Escape Population	No comparisons. all scheduled visits in Maintenance Period	Secondary analysis

Measure	Variable	Estimand (Section 6.2)	Analysis Method (Section 6.1)	Population (Section 6.1.1)	Comparison/Time Point	Analysis Type
	Percentage change in SCORAD (having achieved EASI-75 at W16) from baseline	Maintenance Supportive Estimand (Hypothetical)	ANCOVA with LOCF	Maintenance Primary Population who have achieved EASI-75 at Week 16	Leb 250 mg Q2W vs PBO; Leb 250 mg Q4W vs PBO; all scheduled visits in Maintenance Period	Secondary analysis
Patient-Oriented Eczema Measure (POEM)	Change from baseline in POEM score	Supportive Estimand (Hypothetical)	MMRM with observed data	ITT	Leb 250 mg Q2W vs PBO; Week 16 and all scheduled visits in Induction Period	Secondary analysis
		Maintenance Supportive Estimand (Hypothetical)	ANCOVA with LOCF	Maintenance Primary Population	Leb 250 mg Q2W vs PBO; Leb 250 mg Q4W vs PBO; all scheduled visits in Maintenance Period	Secondary analysis
		NA	Descriptive stats	Maintenance W16 Escape Population	No comparisons. all scheduled visits in Maintenance Period	Secondary analysis
	Proportion of patients having no problem in each domain:	Supportive Estimand (Composite)	CMH analysis with NRI	ITT	Leb 250 mg Q2W vs PBO; Week 16 in Induction Period	Secondary analysis

Measure	Variable	Estimand (Section 6.2)	Analysis Method (Section 6.1)	Population (Section 6.1.1)	Comparison/Time Point	Analysis Type
European Quality of Life–5 Dimensions–5 Levels (EQ-5D-5L)	
 • EQ-5D mobility • EQ-5D self-care • EQ-5D usual activities • EQ-5D pain/discomfort • EQ-5D anxiety/depression 	Maintenance Supportive Estimand (Composite)	CMH analysis with NRI	Maintenance Primary Population	Leb 250 mg Q2W vs PBO; Leb 250 mg Q4W vs PBO; Week 52 in Maintenance Period	Secondary analysis
	Change from baseline in 
 • EQ-5D VAS • EQ-5D-5L UK Population-based index score • EQ-5D-5L US Population-based index score 	Supportive Estimand (Hypothetical)	ANCOVA with LOCF	ITT	Leb 250 mg Q2W vs PBO; Week 16 and all scheduled visits in Induction Period	Secondary analysis
		Maintenance Supportive Estimand (Hypothetical)	ANCOVA with LOCF	Maintenance Primary Population	Leb 250 mg Q2W vs PBO; Leb 250 mg Q4W vs PBO; all scheduled visits in Maintenance Period	Secondary analysis
		NA	Descriptive stats	Maintenance W16 Escape Population	No comparisons. all scheduled visits in Maintenance Period	Secondary analysis
	Change from baseline in PROMIS Anxiety score	Supportive Estimand (Hypothetical)	ANCOVA with LOCF	ITT	Leb 250 mg Q2W vs PBO; Week 16 and all scheduled visits in Induction Period	Secondary analysis

Measure	Variable	Estimand (Section 6.2)	Analysis Method (Section 6.1)	Population (Section 6.1.1)	Comparison/Time Point	Analysis Type
Patient-Reported Outcomes Measurement Information System (PROMIS®)	Change from baseline in PROMIS Depression score	Maintenance Supportive Estimand (Hypothetical)	ANCOVA with LOCF	Maintenance Primary Population	Leb 250 mg Q2W vs PBO; Leb 250 mg Q4W vs PBO; all scheduled visits in Maintenance Period	Secondary analysis
		NA	Descriptive stats	Maintenance W16 Escape Population	No comparisons. all scheduled visits in Maintenance Period	Secondary analysis
Asthma Control Questionnaire (ACQ-5)	Change from baseline in ACQ-5 score	Supportive Estimand (Hypothetical)	ANCOVA with LOCF	ITT with self-reported comorbid asthma	Leb 250 mg Q2W vs PBO; Week 16 and all scheduled visits in Induction Period	Secondary analysis
		Maintenance Supportive Estimand (Hypothetical)	ANCOVA with LOCF	Maintenance Primary Population with self-reported comorbid asthma	Leb 250 mg Q2W vs PBO; Leb 250 mg Q4W vs PBO; all scheduled visits in Maintenance Period	Secondary analysis
Modified Subcutaneous Administration Assessment Questionnaire (SQAAQ)	Proportion of patients who answer “Strongly Agree” or “Agree” in each of 10 questions in a visit	NA	Descriptive stats	Patients who complete SQAAQ at any visit	Leb 250 mg Q2W vs PBO; by sequence of each self/caregiver injection; (note, patient could start self/caregiver injection at any visit, the visits will be aligned as: 1st self/caregiver injection, 2nd self/caregiver injection,...)	Secondary analysis

Abbreviations: ANCOVA = analysis of covariance; CMH = Cochran-Mantel-Haenszel; ITT = intent-to-treat; KM = Kaplan-Meier; Leb = lebrikizumab; LOCF = last observation carried forward; MCMC-MI = Markov chain Monte Carlo multiple imputation; MMRM = mixed model repeated measures; NRI = nonresponder imputation; PBO = placebo; Q2W = every 2 weeks; Q4W = every 4 weeks; VAS = Visual Analog Scale; W = week.

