5.1.3.2. Maintenance Escape Period

[figure not shown]
Patients who do not achieve an IGA of 0 or 1 or an EASI-75 at Week 16, patients received topical or systemic rescue therapy between baseline to Week 16 and those patients not maintaining an EASI-50 response following re-randomization at Week 24, 32, 40, or 48 will be

assigned to an Escape Arm and receive lebrikizumab 250 mg as open-label treatment Q2W through Week 52. Patients not achieving an EASI-50 response in the Escape Arm after 8 weeks of treatment will be terminated from the study.

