6.2.2.1. Maintenance Primary Estimand (Hybrid)

The maintenance primary estimand is a hybrid estimand representing the clinical question of interest: what is the difference between treatment conditions, i.e., Lebrikizumab vs Placebo, in the target patient population, in successful responses or means after 52 weeks achieved without use of systemic rescue medication, without transferring to escape arm, if topical rescue medication were not available and if all patients continued with treatment except those who discontinued due to lack of efficacy?

The maintenance primary estimand is described by the following attributes:

- A. Population: Maintenance Primary Population as described in Section 6.1.1.
- B. Endpoint: apply to all major and other secondary endpoints for Maintenance Period
- C. How to account for intercurrent events (ICEs)
 - a. Subjects who require any use of systemic rescue medication, discontinue treatment due to lack of efficacy after week 16, or transfer to escape arm will be considered as treatment failures, i.e., non-responder, after the ICEs. Therefore, composite strategy is used for these types of ICEs.
 - b. For subjects who require any use of topical rescue medication, a hypothetical strategy will be used to estimate what the treatment effect would have been if

subjects continued with treatment. Therefore, hypothetical strategy is used for these types of ICEs.

- c. For subjects who discontinue treatment due to reasons other than lack of efficacy after week 16, a hypothetical strategy will be used to estimate what the treatment effect would have been if subjects continued with treatment. Therefore, hypothetical strategy is used for these types of ICEs.

D. Population-level summary: difference in response proportions or means between treatment conditions

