6.2.2.2. Maintenance Supportive Estimand (Hybrid)

The maintenance supportive estimand for both continuous and categorical endpoints is a hybrid estimand representing the clinical question of interest: what is the difference between treatment conditions, i.e., Lebrikizumab vs Placebo, in the target patient population, in successful responses or means after 52 weeks achieved without use of systemic rescue medication, without transferring to escape arm, regardless of use of topical rescue medication and if all patients continued with treatment except those who discontinued due to lack of efficacy?

The maintenance primary estimand is described by the following attributes:

- A. Population: Maintenance Primary Population as described in Section 6.1.1.
- B. Endpoint: apply to all major and other secondary endpoints for Maintenance Period
- C. How to account for intercurrent events (ICEs)
 - a. Subjects who require any use of systemic rescue medication, discontinue treatment due to lack of efficacy after week 16, or transfer to escape arm will be considered as treatment failures, i.e., non-responder, after the ICEs. Therefore, composite strategy is used for these types of ICEs.
 - b. For subjects who require any use of topical rescue medication, observed data will be used. Therefore, treatment policy strategy is used for these types of ICEs.
 - c. For subjects who discontinue treatment due to reasons other than lack of efficacy after week 16, a hypothetical strategy will be used to estimate what the treatment effect would have been if subjects continued with treatment. Therefore, hypothetical strategy is used for these types of ICEs.
- D. Population-level summary: difference in response proportions or means between treatment conditions

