Maintenance Supportive Estimand (Hybrid)	Treatment policy: as observed	Composite: Set to baseline	Composite: Set to baseline	Hypothetical: Set to missing	Composite: Set to baseline	MCMC-MI
Maintenance Supportive Estimand for Categorical Endpoints (Composite)	Composite: Set to nonresponder	Composite: Set to nonresponder	Composite: Set to nonresponder	Composite: Set to nonresponder	Composite: Set to nonresponder	NRI
Maintenance Supportive Estimand for Continuous Endpoints (Hypothetical)	Hypothetical: Set to missing	Hypothetical: Set to missing	Hypothetical: Set to missing	Hypothetical: Set to missing	Hypothetical: Set to missing	LOCF

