6.11. Efficacy Analyses

[Table KGAB.6.11](#) includes the description and derivation of the efficacy/health outcomes measures and endpoints.

[Table KGAB.6.12](#) provides the detailed analyses relative to estimands including analysis type, method and imputation, population, time point, and treatment comparisons for efficacy/health outcomes analyses.

Table KGAB.6.11. Description and Derivation of Efficacy/Health Outcomes Measures and Endpoints

Measure	Description	Variable	Derivation / Comment	Imputation Approach if Missing Components
Investigator's Global Assessment (IGA)	The IGA is a static assessment and rates the severity of the patient's AD. The IGA is comprised of a 5-point scale ranging from 0 (clear) to 4 (severe) and a score is selected using descriptors that best describe the overall appearance of the lesions at a given time point.	IGA score	Single item. Range: 0 to 4 0 represents "clear" 4 represents "severe"	Single item, missing if missing.
		IGA [0,1] with ≥ 2 -point improvement	Observed score of 0 or 1 and change from baseline ≤ -2	Missing if baseline or observed value is missing. Single item, missing if missing.
		IGA [0]	Observed score of 0	
		Time to loss of IGA response, i.e., developing an IGA score ≥ 2 with 2 points deterioration of achieved IGA response at Week 16	Date of first time developing an increase in IGA score ≥ 2 compared to Week 16 - date of W16 re-randomization +1	If a patient has not experienced loss of IGA response by completion or early discontinuation of Maintenance Blinded Period or transfer to escape arm, the patient will be censored at the date of their last visit during Maintenance Blinded Period. If a patient has not experience loss of response by the time of systemic rescue during Maintenance Blinded Period, the patient will be censored at the date of systemic rescue.

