	Time to loss of EASI-50	
Date of first time % change from baseline in EASI score > -50 - date of W16 re-randomization +1
	
If a patient has not experienced loss of EASI-50 by completion or early discontinuation of Maintenance Blinded Period or transfer to escape arm, the patient will be censored at the date of their last visit during Maintenance Blinded Period.

				If a patient has not experience loss of response by the time of systemic rescue during Maintenance Blinded Period, the patient will be censored at the date of systemic rescue.
Body Surface Area (BSA)	The BSA assessment estimates the extent of disease or skin involvement with respect to AD and is expressed as a percentage of total body surface. BSA will be determined by the Investigator or designee using the patient palm = 1% rule	BSA score	$BSA_{Total} = BSA_{head\ and\ neck} + BSA_{trunk} + BSA_{upper\ extremities} + BSA_{lower\ extremities}$	N/A – partial assessments cannot be saved.
		Change from baseline in BSA score	Change from baseline: observed BSA score – baseline BSA score	Missing if baseline or observed value is missing.
SCORing Atopic Dermatitis (SCORAD)	
SCORAD is a validated clinical tool for assessing the extent and intensity of atopic dermatitis. There are 3 components to the assessment:
 
 The extent of AD is assessed as a percentage of each defined body area and reported as the sum of all areas, with a maximum score of 100% (assigned as “A” in the overall SCORAD calculation). The severity of 6 specific symptoms of AD (redness, swelling, oozing/crusting, excoriation, skin thickening/lichenification, dryness) is assessed using the following scale: none (0), mild (1), moderate (2), or severe (3) (for a maximum of 18 total points, assigned as “B” in the overall SCORAD calculation). 	SCORAD score	SCORAD = $A/5 + 7B/2 + C$, where A is extent of disease, range 0-100 B is disease severity, range 0-18 C is subjective symptoms, range 0-20	Missing if component A or B or C is missing.
		Change from baseline in SCORAD score	Change from baseline: observed SCORAD score – baseline SCORAD score	Missing if baseline or observed value is missing.
		Percent change from baseline in SCORAD score	% change from baseline: $100 \times \frac{Observed\ score - Baseline}{Baseline}$	
		SCORAD75	% Improvement in SCORAD from baseline $\geq 75\%$: % change from baseline ≤ -75	Missing if baseline or observed value is missing.

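### Time to loss of IGA response censors escape, systemic rescue and lack-of-efficacy discontinuation, which the hybrid maintenance estimands call treatment failures, and the time-to-loss rows have no estimand

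*SAP*

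**What the plan says.** **Event and censoring.** SAP Table KGAB.6.11 dates loss of IGA response at the first increase of at least 2 points over Week 16. The censoring rule begins "If a patient has not experienced loss of IGA response by completion or early discontinuation of Maintenance Blinded Period or transfer to escape arm" and then censors at the last visit in the blinded period. No reason for early discontinuation is distinguished. A patient without loss of response is also caught by a second rule: "by the time of systemic rescue during Maintenance Blinded Period, the patient will be censored at the date of systemic rescue". The EASI-50 row uses the same wording. Time to loss of EASI-75 is an endpoint in Table KGAB.4.1 and has a row in Table KGAB.6.12, but it has no derivation or censoring row in Table KGAB.6.11.

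**Escape.** After re-randomization, SAP 5.1.3.2 sends to the Escape Arm "those patients not maintaining an EASI-50 response following re-randomization at Week 24, 32, 40, or 48". IGA plays no part in this.

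**Estimands.** In SAP 6.2.2.1, patients who use systemic rescue, "discontinue treatment due to lack of efficacy after week 16, or transfer to escape arm will be considered as treatment failures". Its endpoint attribute is stated to "apply to all major and other secondary endpoints for Maintenance Period". SAP 6.2.2.2 says the same on both counts. The two differ only on topical rescue. The primary says "For subjects who require any use of topical rescue medication, a hypothetical strategy will be used"; the supportive says "For subjects who require any use of topical rescue medication, observed data will be used", shown in Table KGAB.6.4 as "Treatment policy: as observed". Both summarize by a difference in proportions or means.

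**Analysis.** Table KGAB.6.12 gives all three time-to-loss rows NA for estimand, with Kaplan-Meier and log-rank. Table KGAB.4.1 lists them as other secondary maintenance endpoints.

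**The concern.** Time to loss of response is where a reader will look for durability. Within one plan, the same three events are failures in the Week 52 response analyses and censoring events in the durability curves, with no reason given and no estimand stated.

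Kaplan-Meier and log-rank assume that patients censored at a given time have the same future risk as those who stay. That is doubtful for patients who leave because they lost EASI-50 or stopped for lack of efficacy. It is only partly doubtful for systemic rescue, because Protocol 6.1 also counts systemic corticosteroids given for another adverse event as rescue.

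At stake is how the IGA curve may be described, not any confirmatory claim.

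**Working it through.** The documents state no figure for these analyses, so there is nothing to reproduce. The check has two parts.

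**1. One patient through three analyses.** Take baseline IGA 3 and EASI 16 (the entry minima in Protocol 4.1), IGA 1 at Week 16, then IGA 2 and EASI 9 at Week 24.

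- EASI change: (9 − 16)/16 = −44%, which is worse than −50%. EASI-50 is lost and the patient meets the escape trigger.
- Loss of EASI-50: event at Week 24. Escape hides nothing here, because the escape trigger is the event, provided that the escape-visit assessment counts as blinded-period data. Only systemic rescue and lack-of-efficacy discontinuation are in effect censored.
- Loss of IGA response: the rise is 2 − 1 = 1, so no event; censored.
- Week 52 IGA analysis, hybrid estimands: after escape the value is set to baseline (Table KGAB.6.4), so IGA = 3, a non-responder.

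Applying the set-to-baseline rule to the IGA endpoint would always give an event. Baseline IGA is at least 3 and Week 16 IGA at most 1, so the rise is at least 3 − 1 = 2. Patients who already had the 2-point rise when they escaped or were rescued count as events under either rule.

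**2. Illustration of size.** Planned numbers, using the 2:1 randomization, the 34.7% IGA rate in SAP 5.2 and the 2:2:1 re-randomization: 400 × 2/3 × 0.347 = 92.5 IGA responders, or about 37, 37 and 18.5 (placebo withdrawal).

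The rates below are assumptions. Let F be composite failure by Week 52 (40% placebo, 15% active), spread equally over Weeks 24, 32, 40 and 48. Let s be the share of failures that are censored because no 2-point rise came first. The curve then shows

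1 − ∏(k=1..4) [1 − (F/4)(1 − s) / (1 − (k − 1)F/4)].

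For F = 0.40 and s = 0.25: 1 − 0.925 × 0.917 × 0.906 × 0.893 = 0.314.

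| s | Placebo curve | Placebo F(1 − s) | Active curve | Active F(1 − s) |
|---|---|---|---|---|
| 0 | 40.0% | 40.0% | 15.0% | 15.0% |
| 5% | 38.3% | 38.0% | 14.3% | 14.3% |
| 10% | 36.7% | 36.0% | 13.6% | 13.5% |
| 25% | 31.4% | 30.0% | 11.4% | 11.3% |
| 50% | 21.9% | 20.0% | 7.7% | 7.5% |

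F(1 − s) is the share with an observed 2-point rise. The curve tracks that share closely. The gap is to the assumed composite rate in the first row.

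*One patient.* With 18 on placebo and failures 2/2/2/1, Week 52 loss is 7/18 = 38.9%. Censoring one failure gives 35.1% to 33.3% depending on the visit, a drop of 3.8 to 5.6 points. With 37 on active and failures 2/2/1/1, the drop is 2.4 to 2.7 points.

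*Between arms.* With constant hazards the composite hazard ratio is ln(0.85)/ln(0.60) = 0.32, and censoring multiplies it by (1 − s active)/(1 − s placebo). Equal shares leave 0.32. Shares of 25% active and 50% placebo give 0.32 × 0.75/0.50 = 0.48; the reverse gives 0.32 × 0.50/0.75 = 0.21.

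*Events.* For one active arm against placebo: 18.5 × 0.40 + 37 × 0.15 = 12.95. At s = 25% this becomes 12.95 × 0.75 = 9.7.

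*EASI-50.* If 30% lose it and a further 3% to 10% have systemic rescue or lack-of-efficacy discontinuation first, the curve shows 30% to 31%, against 33% to 40% for the composite.

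**The case against.** The strongest reply is that the curve does what its name says. A move from IGA 1 to 2 is not the defined event. A censored patient leaves the risk set and is not carried to Week 52 as a success. In the illustration the curve sits at or slightly above the share with a 2-point rise. Pure IGA loss is a legitimate question, and a different hazard ratio under composite counting answers a different question. All of this stands. A reader might infer from 31% against 40% that the curve misreports IGA loss by 9 points; it does not, because 40% is an assumed composite rate.

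Second, NA is understandable: a proportions-or-means summary with multiple imputation does not fit a time-to-event row. The scope sentence is not followed elsewhere either, since SCORAD at Week 52 has only the hypothetical estimand. This weakens any reading that the plan breaches a stated estimand. It does not supply the missing one, and the scope sentence still conflicts with the table.

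Third, escape is visible elsewhere. The Version 4 revision history says that time to loss of EASI-50 was redefined to show how soon patients move to escape. SAP 6.7 counts escapes, SAP 6.10.1 reports rescue by visit, and by-visit IGA maintenance treats escape as failure. This limits the stakes, but none of it corrects the IGA curve, and the revision entry for its censoring rule gives only clarification as the reason.

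**Conclusion.** The point holds, at minor-to-moderate weight. The plan's text classifies the same events as failures in one place and censors them in another, and leaves the time-to-loss endpoints without an estimand. For IGA the censoring is likely informative at escape and at lack-of-efficacy discontinuation. The curve therefore cannot be presented as durability under the plan's failure definition, and relative to that definition it looks more favourable.

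The size is unknown. The documents give no escape or rescue rates, and lack of efficacy is not among the early-termination reasons listed in Protocol 8.7.1. The percentages above rest on assumed values of F and s, and s is lower if 2-point rises are caught at the four-weekly visits before escape.

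Three stronger readings are not supported. The log-rank comparison is not shown to favour lebrikizumab: the effect may be unchanged or move either way. Loss of EASI-50 is not distorted by escape; this relies on the SAP 5.1.3.2 trigger, which Protocol 5.3.3 words differently, so the two should be reconciled. No primary or major secondary conclusion is touched, because these endpoints are outside the testing procedures in SAP 6.6.

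**What to change.** 1. In SAP 6.2.2 add a time-to-event estimand for 'time to loss of response or treatment failure', with its own Kaplan-Meier and log-rank summary and no multiple imputation. Count transfer to escape, first systemic rescue and lack-of-efficacy discontinuation as events on their dates. For the EASI-50 and EASI-75 versions, counting escape is only a safeguard, because losing EASI-50 means that EASI-75 is already lost.
2. State how topical rescue is handled. Using data as observed matches the supportive hybrid. Matching the primary hybrid would mean also censoring at first topical rescue, which Protocol 6.3 permits in maintenance, so it would add censoring.
3. Keep the present censoring as a supplementary analysis. The SAP's Version 2 revision history reserves 'sensitivity' for analyses that handle intercurrent events as the primary estimand does.
4. Add the loss of EASI-75 row to Table KGAB.6.11, and state that escape-visit assessments count as blinded-period data.
5. Replace NA in Table KGAB.6.12, and reconcile the scope sentences in 6.2.2.1 and 6.2.2.2 with the estimands actually assigned row by row.

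**Cost.** Wording, one table row and one event flag; no new data, provided that the reason for discontinuation is recorded. Reported durability becomes somewhat less favourable. The main IGA curve becomes a composite that includes EASI-triggered escape and corticosteroids given for conditions other than atopic dermatitis; the supplementary analysis preserves the pure IGA view.
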